4 SUBJECT SELECTION

4.1 Eligibility Criteria

- Patients with histologically proven prostate cancer and tumors limited to the prostate (including seminal vesicle involvement, provided all visible disease was surgically removed) who have completed local therapy and have an elevated PSA after surgery or rising PSA after radiation therapy, as defined below.
- Age 18 years or older
- Histologically confirmed diagnosis of prostate cancer.
- Previous treatment with definitive surgery or radiation therapy or both.

- No evidence of metastatic disease on physical exam, CT/MRI/CXR (see Section 7.1 for radiologic imaging), and bone scan within 4 weeks prior to randomization.
- Prior neoadjuvant/adjuvant hormonal, androgen deprivation therapy, or chemotherapy is allowed if it was last used > 12 months prior to first vaccination.
- No therapy modulating testosterone levels (such as leuteinizing-hormone releasing-hormone agonists/antagonists and antiandrogens) is permitted within 12 months prior to first vaccination. Agents such as 5 α -reductase inhibitors, ketoconazole, megestrol acetate, systemic steroids (replacement doses of steroids are allowed), PC-SPEs, and Saw Palmetto are not permitted at any time during the period that the PSA values are being collected.
- Hormone-sensitive prostate cancer as evident by a serum total testosterone level > 150 ng/dL or > 6 nmol/L at the time of enrollment within 4 weeks prior to randomization.
- All patients must have evidence of biochemical progression as determined by a reference PSA value followed by 1 confirmatory rising PSA value, higher than the previous value, obtained at least 2 weeks apart. All of these PSA values must be obtained at the same reference lab, and all must be done within 6 months prior to enrollment.
- The most recent of the PSA values must be \geq 2.0 ng/mL. This measurement must be obtained within 1 month prior to enrollment.
- The PSA doubling time (PSA-DT) must be less than 12 months.
- ECOG performance status 0 or 1.
- Patients must have normal organ and marrow function as defined below:
 - Absolute neutrophil count > 1,500/ μ L
 - Platelets > 100,000/ μ L
 - Total bilirubin 1.5 x upper limit of normal (ULN)
 - SGOT (AST) and SGPT (ALT) < 2.5 x institutional ULN
 - Creatinine 1.5 x ULN
- The effects of dendritic cell vaccines on the developing human fetus are unknown. For this reason men must agree to use adequate contraception (hormonal or barrier method of birth control) prior to study entry and for the duration of study participation.

4.2 Exclusion Criteria

- Patients must not be receiving other investigational agents or concurrent anticancer therapy.
- No uncontrolled intercurrent illness including, but not limited to, ongoing or active infection, symptomatic congestive heart failure, unstable angina pectoris, cardiac arrhythmia, or psychiatric illness/social situations that would limit compliance with study requirements.
- Patients must not have active eczema, atopic dermatitis, or other exfoliative skin conditions (e.g., burns, impetigo, varicella zoster, severe acne, contact dermatitis, psoriasis, herpes or other open rashes or wounds).
- Presence of an active acute or chronic infection, including urinary tract infection, HIV or viral hepatitis. HIV patients are excluded based on immunosuppression which may render

them unable to respond to the vaccine; patients with chronic hepatitis are excluded because of concern that hepatitis could be exacerbated by the injections. If clinically indicate, HIV/viral hepatitis testing will be performed to confirm status.

- Patients with a history of auto-immune disease such as, but not restricted to, inflammatory bowel disease, systemic lupus erythematosus, ankylosing spondylitis, scleroderma, or multiple sclerosis. Patients receiving replacement thyroid hormone would be eligible.
- No concurrent use of systemic steroids, except for local (topical, nasal, or inhaled) steroid use. Adrenal replacement doses of corticosteroids are allowed.
- Subjects with concurrent additional malignancy (with exception of non-melanoma skin cancers and superficial bladder cancer or malignancy within last 3 years).

4.3 Gender/Ethnicity

Study entry is open to male patients of all ethnic backgrounds. The racial and ethnic characteristics of the proposed subject population will reflect the demographics of Pittsburgh and the surrounding area and/or the patient population of the UPMC Health Systems. We shall attempt to recruit subjects in respective proportions to these demographics. No exclusion criteria will be based on race, ethnicity, gender, or socioeconomic status. In recent Phase I/II trials at UPCI, approximately 11% of subjects were non-caucasian. Given the limited size of the patient population to be accrued on this trial, there will be limited power to determine differences in efficacy between different racial groups. However, we will describe any apparent differences in efficacy or toxicity.

4.4 Subject Recruitment

Approximately 12-16 subjects are expected to enter the study. All of whom will be accrued through the University of Pittsburgh Cancer Institute.

For the proposed trial, all the subjects will be accrued at UPCI Hillman Cancer Center. There is an extensive clinical practice in urologic cancers between the Medical Oncology offices and the Urology offices at UPCI/UPMC. In addition, UPCI has vast community links and a large clinical investigations program through its economically aligned network of over 60 medical and radiation oncologists who practice in community-based sites throughout western PA and adjacent areas of Ohio and West Virginia. In the UPMC/UPCI Network registry for Genitourinary Organs, 2004-2005, 1117 new cases of prostate cancer were diagnosed across the system hospitals. Across the entire state of Pennsylvania, 10,300 new cases of prostate cancer are expected to be diagnosed this year. At current rates, we expect one out of every 6 will be seen in the UPMC/UPCI network. Since most of these patients are referred to UPCI for novel clinical investigations, we expect rapid accrual to the above protocol. In the last 2 years, over 125 subjects/year have been accrued to clinical trials in the UPCI prostate cancer program.

Potential subjects will be approached by clinicians who are directly involved in their care. "Cold-

calling” will not be used to recruit subjects and “Finder’s fees” for referring a potential subject for participation in a research study are prohibited. Physicians and other health care professionals in the area are aware of active studies at UPCI by means of various publications including the World Wide Web. Such publications and Web listings are not advertisements for specific studies. Rather, they are public listings of trials available. Subjects will *not* receive any monetary compensation for participation.

5 STUDY DESIGN AND METHODS

This is a 2 group crossover trial in which subjects are randomly assigned to one of two treatment arms:

Cohort A: 3 months of androgen ablation (AA) to be followed at PSA progression by 3 months of the combination of AA and alpha-type 1 dendritic cell vaccine (DC1).

Cohort B: 3 months of the combination of AA and alpha-type 1 dendritic cell vaccine followed at PSA progression by 3 months of AA.

In this crossover trial each subject will serve as their own control. Following either therapy the time to PSA progression is defined as the time between treatment and the first instance of PSA increase to 1 ng/mL. The endpoint is the difference between the time to PSA progression for the combination of AA + DC1 compared to AA alone. A **total of 12 evaluable subjects** (6 subjects/arm) will be enrolled on the trial. Subjects who do not complete both courses (AA and AA+DCV) will be replaced. This schema will also help us better estimate the time to PSA recovery following 3 months of limited androgen ablation in our cohort of subjects.

All subjects in Cohort B will commence α DC1-based vaccination 2 weeks prior to treatment with the LHRH analogue. Each subject will receive 1 intradermal (*i.d.*) dose of the vaccine at weeks 1, 5, 9, and 13 for a total of 4 doses. The first dose will be considered the ‘priming’ dose and injections on weeks 5, 9, and 13 are ‘booster’ doses. Depending upon cells/volume the injections may utilize 1-2 syringes being administered on a single day. Additional courses of vaccination, if available after the 4 intended protocol doses, can be administered to any subject without evidence of disease progression, every 3 months (\pm 1 month) for up to 12 months. The schema for the vaccine can be found on page 6.

The LHRH analogue (Lupron 22.5 mg or Zoladex 10.8 mg) will be administered 2 weeks after the 1st dose of the DC vaccine.

We assume that 3 months of AA alone will be followed by PSA progression at a median of 6 months with 90% of PSA recovery times between 5 and 7 months. We suspect that a second course of AA will delay time to testosterone recovery by approximately 10% and that testosterone recovery and PSA failure will likely correlate very closely. Therefore we anticipate that a second course of AA will delay time to PSA relapse by approximately 10%. The purpose of randomizing to one of two treatment sequences is to permit an unbiased estimate of

the improvement due to DC1 treatment effect in the presence of any 2nd course variability. In this study, on treatment PSA-relapse is defined as a PSA \geq 1.0. We consider the clinically significant objective to be a within-subject delay in PSA progression time due to the addition of DC1 by 30% or to 7.8 months.

Our estimates of time to testosterone and PSA recovery are based on a recent study that we participated in (Figg et al, Lancet Oncology [*in press*]; Figg et al, ASCO Proceedings, 2008, Abstract #5015).

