With respect to immunotherapy, since it is known that androgen ablation promotes an influx of T cells into the prostate (Mercader et al., 2001), in the proposed trial we plan on immunizing men in concert with limited (3 months) androgen ablation. We plan on introducing androgen ablation 2 weeks after immunization, in order to focus the effector phase of prostate cancer-specific immune response on the existing prostate cancer sites. We anticipate that such timing of both treatments will allow the circulating inflammatory-type cancer-specific T cells (Th1 cells and CTLs) induced by the first dose of the α DC1-based vaccine, to enter the existing tumor sites damaged by the hormone therapy and to eliminate the surviving cancer cells. The second dose of the vaccine, administered 2 weeks after the hormone therapy and the 2 remaining vaccine doses,

are anticipated to re-enforce such an effect, cumulatively prolonging the time to disease progression, compared to what is typically observed after limited androgen ablation: PSA recurrence, as testosterone levels recover in 3 to 6 months. Thus, we hypothesize that the combination of the α DC1-based vaccine and limited androgen ablation, will significantly delay time to PSA recurrence, despite a normalization of testosterone levels. Finally, we also anticipate that the combination treatment proposed above, will further enhance the activity of vaccination by counteracting tumor-related, prostate-specific immune tolerance, that has been demonstrated in experimental murine models of prostate cancer (Drake et al., 2005).

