Thus, our goal is to develop protocols to induce autoimmune prostatitis as a novel immunotherapy for prostate cancer, through dendritic cell-induced stimulation of $CD8^+$ cytotoxic T cell (CTL) responses against prostate autoantigens. This is based on the premise that a vigorous autoimmune response against prostate-specific proteins, capable of destroying normal prostate tissue, will also destroy malignant prostate tissue, provided the malignant tissue expresses these proteins. Since the prostate gland is routinely removed or ablated as a part of the treatment for early prostate cancer, any remaining/recurring prostatic tissue could be destroyed immunologically. Three prostate tissue specific antigens are currently being evaluated in clinical trials: prostate specific antigen (PSA), prostatic acid phosphatase (PAP), and prostate specific

membrane antigen (PSMA). However the immunogenicity of these proteins is not well understood, and a priori, there is no perfect prostate-specific immunologic target. Hence our focus is on the allogenic tumor cell line - LNCaP. Additionally, we will also incorporate limited (3 months) androgen deprivation (with LHRH analogues) in the treatment protocol to enhance the immune-potentiating effects of this manipulation, as described above (Drake et al., 2005; Mercader et al., 2001).

Our target population for treatment will be men with prostate cancer, who have relapsed following surgery and/or radiation, and now have a rising PSA with a PSA doubling time (PSA-DT) of less than 10 months. This patient population is **ideal for an immunologic intervention** given that: i) this is the largest sub-population of men with prostate cancer in the U.S.; ii) there is no standard treatment for this sub-group; and iii) this sub-group has minimal systemic disease burden (Havranek et al., 2002; Kaufman et al., 2004). We will carefully monitor immunological responses to vaccination at different time points, but the primary endpoint of vaccine efficacy will be stabilization of PSA levels or failure of the PSA to progress. Several recent studies have validated failure of PSA progression as a good surrogate endpoint for lack of progression in clinical trials in prostate cancer (Scher et al., 2004).

This is a 2 group crossover trial in which subjects are randomly assigned to one of two treatment arms:

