9.3 Characteristics of the Design

The difference in PSA progression between AA and AA + DCV will be calculated for each individual subject. We note that if the standard deviation of this difference is 1.5 months, a one tailed signed rank test at $\alpha = .05$ will have 98% power to detect a improvement of 1.8 months, equivalent to a hypothesized 30% improvement in time to PSA recovery (6 months vs 7.8 months).

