9.5 Data Analysis

Subjects will be required to have monthly PSA monitoring. This will enable linear interpolation between PSA samples to detect the time at which PSA progression occurs following each course of therapy. The efficacy endpoint is estimated by the difference between time to PSA progression for the AA+DCV arm and the AA arm. This difference will be tested for significance with a one tailed signed rank test. Other conventional estimates of clinical efficacy will also be calculated including PSA doubling time and PSA velocity. The PSA-DT will be calculated as follows:

The logarithm of a minimum of two PSA measurements will be plotted against the time of each PSA measurement. If 3 or more measurements are available a linear regression equation will be estimated. Two sequential PSA measurements (actual or estimated by linear regression) will be denoted as PSA1 and PSA2. Denote their times of blood samples as t1 and t2, respectively. Thus the PSA doubling time is: $\log(2)[t2 - t1] / [\log(\text{PSA}2) - \log(\text{PSA}1)]$.

Further analysis will involve testing the immunologic response of subjects receiving the α DC1-based vaccine. The principal measure of improved immunogenicity will be the comparison of pre to post α DC1-based vaccine T cell response to prostatic acid phosphatase (PAP) as measured by the IFN- γ Elispot assay. We expect that prostate cancer subjects undergoing androgen ablation in the absence of immune stimulation will have a negative or very low Elispot count for measuring reaction to PAP. Even with a nominal count of 5 spots in the group, a sample of 7 subjects with androgen ablation alone and 7 subjects treated with androgen ablation + α DC1-based vaccine will provide 90% power to detect a difference of double the Elispot count (average of 5 to 10 spots) using a one tailed alpha level Wilcoxon test if the Elispot counts have a Poisson distribution. Additional immunologic testing will be conducted by analyzing subject profiles before treatment and after each course of therapy. Immunologic endpoints include T cell reactivity by IFN γ or IL-5 Elispot, cytokine release assays for cytotoxicity and DTH tests (as measured by induration in mm). Changes over time will be tested with the Friedman Test or, if there are missing values, the Mack-Skillings procedure.

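### A man who does not relapse after his first course has no place in the paired efficacy test, so entry to that test depends on outcome and on sequence

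*Combined protocol and SAP*

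**What the plan says.** Section 5 describes a two-sequence crossover. Cohort A has AA alone and then AA plus vaccine; Cohort B has the reverse. In both, the second course begins at PSA progression. The target is a "total of 12 evaluable subjects", six per arm, and "Subjects who do not complete both courses (AA and AA+DCV) will be replaced". No reason for non-completion is excepted.

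Section 9.3 defines the unit of analysis: "The difference in PSA progression between AA and AA + DCV will be calculated for each individual subject". Section 9.5 gives the test: "This difference will be tested for significance with a one tailed signed rank test". Neither section gives a censoring rule, a maximum observation time, a data cut-off or an analysis of all randomised men.

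The plan does foresee men who do not progress. Section 5 says that further vaccine "can be administered to any subject without evidence of disease progression, every 3 months", if doses remain. Section 7.3 allows men without progression 12 months after the last treatment to be monitored, but for disease-free and overall survival. Section 3 hypothesises that the combination "will significantly delay time to PSA recurrence, despite a normalization of testosterone levels", and in one place states that "the primary endpoint of vaccine efficacy will be stabilization of PSA levels or failure of the PSA to progress". None of this is tied to the paired endpoint.

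Section 5 gives the reason for randomising the sequence: an unbiased estimate of "the improvement due to DC1 treatment effect in the presence of any 2nd course variability".

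**The concern.** A Cohort B man who stays below the PSA threshold after AA plus vaccine never starts AA alone. He has one progression time at most, no difference, and falls under the replacement rule. He has the best result the vaccine can produce, and the efficacy test cannot count it. A Cohort A man who does not relapse after AA alone is lost in the same way, with the opposite effect. A Cohort A man who does not relapse after the vaccine has had both courses, but his second time is censored and no rule covers him.

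Membership of the efficacy set is therefore decided partly by outcome, and differently in the two sequences. Losing Cohort B non-relapsers works against the vaccine; losing Cohort A men who do not relapse after AA alone works for it. Men removed for toxicity (sections 6.3 and 6.4) could shift the result either way. The net direction is unknown. With 12 men, one or two durable responders could be the main signal of the trial.

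**Working it through.** **1. The plan's own power.** Inputs from section 9.3: mean difference 1.8 months, SD 1.5, one-tailed signed-rank test at 0.05; 12 subjects from section 9.2. The exact test rejects when the positive rank sum is at least 61 (exact alpha 0.046). Simulated power with normal differences is 98.2%, which agrees with the stated 98%. The calculation assumes 12 complete pairs.

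**2. How many men are affected under the planning figures.** Section 5 puts 90% of AA-alone times between 5 and 7 months, so the AA SD is 1/1.645 = 0.608 if times are normal. With independent times, the vaccine-time SD is √(1.5² − 0.608²) = 1.371 about a mean of 7.8. The chance that a vaccine time passes 12 months is P(Z > 4.2/1.371 = 3.06) = 0.1%. If a man's two times correlate at 0.5, the vaccine SD is 1.71 and the chance is 0.7%. AA times are further still from 12 months (6/0.608, nearly 10 SDs above their mean).

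**3. Bias under the planning figures.** If Cohort B men past 12 months are replaced, the mean gain in those retained is 1.795 months. Averaged with 1.8 in Cohort A it is 1.80, and power stays at 98%. Limits of 9 or 10 months would give 1.57 or 1.72 (independent times), but the documents set no such limit.

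**4. If some men have durable control.** The documents give no rate, so shares of 10%, one sixth and one third are assumed. Relapsers' differences are normal with SD 1.5 and the mean gain shown. Each cell gives power with all non-relapsers ranked highest / Cohort B non-relapsers replaced and Cohort A's ranked highest / neither usable.

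| Share not relapsing after vaccine | Gain 0 | Gain 0.9 months | Gain 1.8 months |
|---|---|---|---|
| 10% | 12 / 8 / 5% | 71 / 65 / 59% | 99.0 / 98.6 / 98.2% |
| One sixth | 20 / 10 / 5% | 78 / 69 / 59% | 99.3 / 98.9 / 98.2% |
| One third | 50 / 19 / 5% | 91 / 78 / 59% | 99.8 / 99.4 / 98.2% |

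At a 10% share, the chance that at least one of six Cohort B men is lost is 1 − 0.9⁶ = 47%.

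**5. Why a repair must account for sequence.** Section 5 expects a second course to delay relapse by about 10%, that is δ = 0.6 months on 6. With vaccine effect τ, the vaccine-minus-AA difference centres on τ + δ in Cohort A (vaccine second) and τ − δ in Cohort B. With τ = 0 the pooled mean is δ(nA − nB)/(nA + nB):

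- 6 v 6: 0
- 8 A v 6 B: 0.6 × 2/14 = 0.09 months
- 10 A v 6 B: 0.6 × 4/16 = 0.15 months

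Simulated one-sided type I error of the pooled signed-rank test (SD 1.5) is about 3.6%, 5.2% and 7.8%. Section 4.4 expects 12 to 16 entrants, so such imbalances are possible. If course-2-minus-course-1 differences are compared between cohorts instead, they centre on δ + τ and δ − τ. The gap is 2τ and the delay cancels.

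**The case against.** The strongest reply is that the gap is narrow and the large numbers are assumed. Section 8.3 expects relapse within 5 to 7 months as testosterone recovers, and the objective is a delay to 7.8 months, not cure. PSA is drawn every four weeks after week 21 with no stopping point, so a late relapser can still cross over and be paired. The 50% v 19% contrast needs one third of men with durable control and no gain at all in the rest. The wording about failure to progress is rationale; sections 1.1, 5, 8.1 and 9.1 make time to PSA progression the operative endpoint. Section 9.1 calls the efficacy estimate preliminary, and section 9.2 sizes the trial for feasibility and safety.

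Most of this stands, and it limits the size of the point. It does not remove the point: efficacy is a primary objective in section 1.1, a formal test is specified, and the stated rules lead to exclusion by outcome.

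Three stronger readings are tempting and not supported:

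- **Replacement alone is the cause.** Crossover at relapse and an uncensored paired test would leave these men without a difference even if nobody were replaced. The documents also never say outright that replaced men leave the efficacy analysis; this follows from a paired test on evaluable subjects.
- **The plan loses men at 9 or 10 months.** No section sets such a limit.
- **The signed-rank test cannot use these men.** It can, once a rank rule is written.

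**Conclusion.** The concern holds in a limited form. Crossover at relapse, a paired test without a censoring rule, and replacement together make entry to the efficacy set depend on outcome and sequence, against the stated purpose of randomising the sequence.

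Under the planning assumptions with 12 months of observation, the consequence is negligible. A reader might infer that the 98% power is wrong or that the trial is materially biased against the vaccine. The documents support neither.

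The rule matters if some men have durable control and relapsers gain less than planned. At a gain of 0.9 months, replacing Cohort B non-relapsers costs about 6 points of power at a 10% share and 13 at one third. With no gain in relapsers it costs 4 and 31 points. At the full 1.8 months it costs under 1 point. The shares, the normal differences and the ranking of Cohort A non-relapsers as highest are assumptions. The table does not model Cohort A men who do not relapse after AA alone. This is worth fixing before results are known, so that handling is not chosen after seeing who did not relapse.

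**What to change.** Amend section 5 (replacement) and section 9.5:

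1. A subject who started course 1 and has not progressed stays in the efficacy analysis and is not replaced for that reason.
2. Set one analysis limit, the same for both courses and both cohorts and counted from the same origin (for example 12 months), and cap both times at it. Cut the data when every man in follow-up has progressed or reached the limit in his latest course. The limit governs the analysis only and does not change when course 2 starts.
3. A man without progression at the limit in course 1, and so without a second-course time, gets the largest rank: positive if course 1 was AA plus vaccine, negative if AA alone, ties shared. Two capped times give a zero difference.
4. Make the test account for sequence whenever cohort sizes differ. A rank comparison between cohorts of course-2-minus-course-1 differences removes the second-course delay (step 5); men under item 3 then take the lowest value in either cohort. If a stratified signed-rank test is preferred, the cohorts must carry equal weight, because simply adding two within-cohort rank sums leaves the larger cohort's delay in the total.
5. Add an all-randomised comparison of first-course time to progression as supporting analysis (a one-sided rank-sum test of 6 v 6 has 82% power at 6 v 7.8 months), and report the completers' signed-rank test as sensitivity.
6. Reconcile sections 6.3, 6.4 and 7.4 on whether PSA follow-up continues after a man comes off treatment.

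**Cost.** Protocol and SAP wording, and perhaps a few more PSA draws. Some ranks are assigned rather than observed, so the effect should be reported as a median or rank-based estimate. With equal cohorts, the capped signed-rank rule keeps 98% power under the planning figures (97% with the 10% second-course delay, 12-month limit). It is somewhat conservative: type I error is 2.8% to 4.7% with one sixth to one third not relapsing. The read-out may come later.
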